# 8. Methods Collection, administration and data analysis

#### 8.1 Methods of data collection

A clinical monitor will be assigned to each research center, which will be authorized to monitor, review, procure and ensure that the quality of the information obtained from the participants is reliable and trustworthy. Each monitor will schedule periodic visits to the research centers in order to review the source documents and corroborate the information captured in the case report format (CRF). All clinical monitors will be trained in relation to the information of the study protocol (objective, visits, procedures, range of accepted values, etc.). In the event that the data are not identical between the two registers, the clinical monitor will generate a discrepancy, which must be resolved by the research center in time that the sponsor deems reasonable to meet the objectives of the clinical study. The correction of the discrepancies will be made according to the Good Documentation Practices.

The data registered in the CRF will be reviewed by personnel of Sophia Laboratories SA de CV, trained in the ophthalmological, clinical and pharmacological area, which will have the power to generate discrepancies in the event that the data do not comply with the stipulations of the research protocol or put participants at risk.

Once all discrepancies generated by the team of clinical monitors and clinical staff have been resolved, the data will be downloaded into an electronic database (Excel Sheet) by personnel

#### CONFIDENTIAL

designated by the sponsor. A new review of the data will be carried out to corroborate the fidelity of the same and new discrepancies may be generated in case it was considered.

The database generated will be safeguarded by the sponsor and will only have personal access designated by the same.

#### 8.1.1 Strategies to complete the follow-up

- You will be clearly informed of the importance of the study and the benefits that the population will obtain from the results of the study.
- Transportation assistance will be provided in order for the participant to attend their visits.
- Calls, messages or a printed calendar will be made in order to remind the participant of their appointments and the activities that will be carried out, in addition to the estimated duration of the same.
- In case the participant does not attend his appointment, the research center must make a call to know the reason and try to arrange a new appointment within the established window period or an unscheduled appointment.
- In case it is not possible to make an appointment, it will be asked about the presence of adverse events and the reason for leaving the study, as minimum data.

#### 8.2 Data management

The subject's medical record (including clinical notes, test results, etc.), the subject's diary, and the ICO questionnaire are considered source data.

The PI or the designated person of your team will fill out the Case Report Format (CRF) with all other documents provided by the sponsor (for example, documents related to the handling of the treatment).

A CRF was designed to record the data that are required in the protocol and that the researcher collects in each of the visits.

In the case of self-assessment questionnaires, it is not permissible for the principal investigator or person responsible for filling in to modify what was written by the subject of the study.

The data capture in the investigator's site will be done by the investigator or the designated person of his team after performing the Medical File. The researcher or a designated person of your team will be trained in filling the CRF.

All corrections to the CRF data should be made by the investigator or the designated person of your team in accordance with the instructions provided.

To ensure the confidentiality and security of the data, user names and access codes will be used to restrict access to the system only to authorized personnel.

The monitor must ensure that all the data has been filled in the CRF. After comparing the data against the source documents, the monitor will ask the researcher to make the necessary correction / clarification, so that they are answered and closed as quickly as possible.

The Scientific Committee of Laboratories Sophia S.A. of C.V. will give the latest medical-scientific review, and will set the pattern to freeze the database.

#### 8.3 Statistical methodology

#### 8.3.1 Analysis of primary and secondary outcome variables

The statistical analysis will be carried out by personnel of Sophia Laboratories. The statistical program SPSS version 19 (IBM Corporation, Armonk, NY, USA) will be used.

The designated personnel will be blinded to the intervention groups. The coding will be done using consecutive numbers for each intervention group.

The data will be collected and sorted in an excel sheet. Later they will be exported to the platform of the SPSS program. The variables will be categorized according to their nature.

The result of the continuous quantitative variables will be presented in measures of central tendency: mean, standard deviation and ranges. See Table 4. Scales to be used

The normal distribution of the results will be obtained by the Kolmogorov-Smirnov test.

The statistical analysis of the continuous **quantitative variables** to find significant differences (p) will be the following:

- Intra-group analysis: Wilcoxon rank test.
- Inter-group analysis: Mann-Whitney U test.

The level of difference to consider significance will be an alpha of 0.05 or less.

The result of nominal and ordinal qualitative variables will be presented in frequencies, proportions and percentages.

The statistical analysis to identify significant differences of the **qualitative variables** will be done creating 2x2 contingency tables and it will be carried out in the following way:

- Intra-group difference: McNemar or Pearson test.
- Difference between groups: test χ2 (Chi-square) of Pearson.

The level of difference to consider significance will be an alpha of 0.05 or less.

For the reporting of adverse events all eyes of those participants who were randomly assigned to an intervention group after the baseline visit will be considered. The results will be expressed in number of cases (eyes).

The final report of the results will be shown in tables or graphs, as appropriate.

It will be considered that the investigational drug is safe and tolerable when there are no clinical and statistical differences in all the variables of primary outcome, with respect to its comparator.

Those subjects who comply with an adherence greater than 60% will be included in the statistical analysis to meet the objective of the study. It was considered that from the minimum dose necessary to obtain a pharmacological effect (reepithelizer / 1 cm per day) and the presence of adverse events (exposure) is sufficient to meet the overall design objective, according to the pharmacological characteristics of the product in investigation.

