#### 5.5.2 Specific objectives

- Describe the safety of the ophthalmic gel PRO-167 by means of the density of goblet cells
- Describe the safety of the ophthalmic gel PRO-167 by means of changes in ocular surface stains.

- Describe the safety of the ophthalmic gel PRO-167 by means of changes in intraocular pressure.
- Describe the safety of the ophthalmic gel PRO-167 by means of changes in laboratory tests.
- Describe the safety of the ophthalmic gel PRO-167 by means of changes in vital signs.
- Describe the safety of the ophthalmic gel PRO-167 by means of changes in visual ability.
- Describe the safety of the ophthalmic gel PRO-167 by means of changes in the time of tear rupture.
- Describe the safety of the ophthalmic gel PRO-167 by means of changes in the ocular comfort index.
- Describe the safety of the ophthalmic gel PRO-167 by means of changes in the posterior segment.
- Describe the safety of the ophthalmic gel PRO-167 by means of changes in ophthalmological signs and symptoms.
- Describe the safety of the ophthalmic gel PRO-167 when assessing the integrity of the anterior segment by means of the green lysine stain.
- Describe the safety of the ophthalmic gel PRO-167 by means of the presentation of adverse events.

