#### 6.5.1.2 Basal visit

- Review of laboratory tests: refers to the review and analysis by the IP of the results of the BH, QS and PFH. See 6.4.3.12 Laboratory tests.
- Eligibility criteria: with the laboratory results, the subject's profile will be finalized for inclusion or not.
- Assignment: It refers to determining the intervention that the patient will follow during the study. It will be done according to section 7. Methods. Assignment of the intervention. This assignment will be made at the baseline visit (day 0) and will go along with the indication to start the treatment period the next day (day 1).
- Delivery of intervention: Refers to the delivery of the product under investigation to the patient of the study, by the research center. It will be done according to sections 6.3.1 Managed treatments and 6.3.4.1 Delivery and reception.
- Evaluation of variables: The data of the evaluation of the variables listed below can be taken from the scrutiny visit, as long as it does not exceed 7 days prior to this visit. It is the IP's prerogative to decide whether to use the information from the screening visit or to repeat the evaluations on this visit.
  - o Intraocular pressure
  - o Visual capacity
  - o TRL
  - o Epithelial defects (TF and TVL)
  - o Eye signs and symptoms
  - o Subsequent segment
  - o vital signs

- Eye comfort index: see 6.4.3.3 Eye comfort index
- Density of goblet cells (cytology per impression): see 6.4.3.2 Density of goblet cells (cytology per impression)
- Delivery of the subject's diary: It refers to the delivery by the IP to the subject, the subject's daily instrument.
- Delivery of quality questionnaire: It refers to the delivery by the IP to the subject, the quality questionnaire instrument.

#### 6.5.1.3 Visit 1

- Intervention delivery: see 6.5.1.2 Baseline visit
- Return of intervention: refers to the return of research products to the center by the research subject.
- Evaluation of adherence: refers to the assessment made by the IP according to section 6.3.2.1 Procedure to monitor adherence
- Adverse events: see 6.4.3.5 Presence of adverse events
- Intraocular pressure: see 6.4.3.6 Intraocular pressure
- Visual ability: see 6.4.3.1 Visual capacity
- TRL: see 6.4.3.10 Rupture time of the tear film
- Epithelial defects (TF and TVL): see 6.4.3.4.1 Stains
- Eye signs and symptoms: see 6.4.3.4 Eye surface integrity: and 6.4.3.9 Ocular symptomatology

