#### 6.6.1 Calculation of the sample size

Although there are no references on the calculation of the sample size in phase I studies, it was considered pertinent to perform it according to the presentation of adverse events referred by Christ T, in a randomized controlled trial of parallel groups, single blind, with randomization where

it was evaluated the efficacy and tolerance of a 5% dexpanthenol ophthalmic gel versus a 5% panthenol ointment in 48 subjects with corneal erosion, keratoconjunctivitis by UV radiation or similar conditions. The intervention consisted in the application of 1 cm of the gel and the ointment during 4 and 3 days, respectively. [20]

The percentage of good tolerance that was presented with the gel was 25%, so it is expected that no more than 10% of the subjects report a bad tolerance with the formulation proposed in this protocol.

The sample size was calculated using the formula for proportions

$$n = p (1 - p) \left( \frac{Z_{1-\alpha + Z_{1-\beta}}}{p - p0 - \delta} \right)^2$$

With a statistical confidence of 95% corresponding to the type I error, equal to 1.96, with a power of 80%, corresponding to the type II error, equal 0.84.

According to the previous calculation, the result is 19 subjects, which was increased by 20% for the probable losses. The total sample size required is 24 subjects. Therefore, each group will consist of 12 subjects, who will provide an eye for analysis.

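### The between-group test for continuous outcomes does not say whether final values or changes are compared, and it makes no baseline adjustment although baseline is collected

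*Combined protocol and SAP*

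**What the plan says.** Section 8.3.1 assigns two methods to continuous quantitative variables. Within arms it is "Intra-group analysis: Wilcoxon rank test"; between arms it is "Inter-group analysis: Mann-Whitney U test". The Summary repeats Mann-Whitney for quantitative variables in general. No covariate is named anywhere in the plan. On the error rate: "The level of difference to consider significance will be an alpha of 0.05 or less".

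The same section calls the product safe and tolerable if the primary outcomes show no clinical and statistical difference from the comparator.

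Section 5.5.2 words several objectives in terms of change, for example "Describe the safety of the ophthalmic gel PRO-167 by means of changes in the ocular comfort index". Intraocular pressure (IOP) and tear break-up time are worded the same way. The goblet cell objective refers to the density itself, not to its change.

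The schedule in section 6.5 places goblet cell density and the comfort index at the basal and final visits. IOP and tear break-up time are measured at the basal visit, or carried over from a screening visit no more than 7 days earlier, and again at visit 1 and the final visit. On allocation, section 6.5.1.2 says "This assignment will be made at the baseline visit (day 0"), and treatment begins on day 1.

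**The concern.** A two-sample Mann-Whitney test takes no covariate. Baseline can enter the comparison of arms only if the test is run on changes, and section 8.3.1 does not say that it is. This has two consequences.

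- **Precision.** On final values, a chance baseline imbalance between two groups of 12 passes into the result. On changes, baseline is over-corrected when its correlation with the final value is low. Because finding no difference counts as safety, imprecision favours the product.
- **An open choice.** The analyst is blinded to arm, but need not know which arm is which to see whether the final-value or the change version shows no difference.

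**Working it through.** **The plan's own figure.** Section 6.6.1 derives 19 subjects from a proportions formula and raises this to 24 for 20% losses. The second step reproduces: 19 / (1 − 0.20) = 23.75, so 24. The 19 does not, because no value is given for δ. With p = 0.10, p0 = 0.25 and δ = 0 the formula gives 0.10 × 0.90 × (2.80 / 0.15)² = 31.4. That is a separate matter. The calculation concerns tolerance proportions and says nothing about precision for continuous outcomes.

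**Inputs from the documents.** There are 12 subjects per group (section 6.6) with 1:1 allocation (section 7.1). Alpha is 0.05, taken as two-sided because section 6.6.1 says "With a statistical confidence of 95% corresponding to the type I error, equal to 1.96". The power term is 0.84 (section 6.6.1).

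**Assumed inputs.** The true difference is 1 SD, the data are normal with equal variance at baseline and final visit, and the baseline-final correlation r ranges from 0 to 0.7. The documents give none of these.

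**Variance of the between-group difference, relative to final values**

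- Change score: 2(1 − r) = 2.00 / 1.40 / 1.00 / 0.60 at r = 0 / 0.3 / 0.5 / 0.7. It breaks even with final values at r = 0.5.
- ANCOVA: 1 − r² = 1.00 / 0.91 / 0.75 / 0.51, before a small-sample penalty for estimating the slope of about 1 + 1/(24 − 4) = 1.05.

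**Difference detectable with 80% power** (normal approximation, penalty ignored)

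- Unadjusted: (1.96 + 0.84) × √(2/12) = 1.14 SD.
- Adjusted: 1.14 × √(1 − r²) = 1.09, 0.99 and 0.82 SD at r = 0.3, 0.5 and 0.7.
- Losses or the 60% adherence filter would make this worse. At an assumed 10 per group the unadjusted figure is 2.80 × √(2/10) = 1.25 SD.

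**Simulated power at 12 per group, 1 SD difference, normal data**

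| Analysis | r = 0 | r = 0.3 | r = 0.5 | r = 0.7 |
|---|---|---|---|---|
| Mann-Whitney, final values | 60% | 61% | 61% | 61% |
| Mann-Whitney, change | 34% | 47% | 62% | 83% |
| Rank ANCOVA | 60% | 64% | 72% | 85% |
| ANCOVA | 61% | 67% | 76% | 89% |

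Repeat runs of 4,000 to 6,000 data sets per setting agree to within about 2 percentage points. With no true difference, all four methods rejected in about 4 to 6% of runs.

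**Reading the table**

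- Against final values, rank ANCOVA gains about 0, 3, 11 and 24 points (rank method against rank method).
- Against changes, rank ANCOVA gains 26, 17, 10 and 2 points. At r = 0.85 the two are level (97% and 98%).

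**Skewed data.** With log-normal data ANCOVA loses some of its edge: 56% against 60% for Mann-Whitney on final values at r = 0, and 67% against 62% at r = 0.5. Rank ANCOVA held at 60% and 71%.

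**The case against.** The strongest reply is that this is a matter of efficiency, not an error. The trial is an exploratory phase I study, its specific objectives are descriptive, its size rests on a proportion, and the planned test holds its type I error. All of that stands.

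Three further points also stand.

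- **The gain is conditional.** It depends on a correlation the documents do not report. Healthy-subject limits such as IOP of 11 to 21 mmHg may lower that correlation, and so may carrying screening values forward for up to 7 days.
- **The reach is limited.** Only goblet cell density and the comfort index enter the safe-and-tolerable rule; IOP and tear break-up time are secondary. Adverse events, graded epithelial defects and symptoms are untouched. Table 4 types the comfort index as discrete. It is reasonable to include it all the same, because section 6.4.3.3 describes a 0-100 interval scale and the Summary applies Mann-Whitney to quantitative variables generally.
- **Baseline is not the only free source of precision.** IOP and tear break-up time are also measured at visit 1.

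A reader might infer that the plan ignores baseline. The documents do not support that: section 5.5.2 speaks of changes for three of the four variables, and a Mann-Whitney test on changes would use baseline. What can be shown is that the tested quantity is undefined.

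A reader might also take 1/(1 − r²) as the equivalent gain in sample size: 1.10, 1.33 and 1.96 at r = 0.3, 0.5 and 0.7. That is a large-sample figure. Dividing by 1.05 gives about 1.05, 1.27 and 1.87.

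**Conclusion.** The point holds as a recommended improvement. Section 8.3.1 leaves the tested quantity open and makes no baseline adjustment, although the data for one are already scheduled.

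For a 1 SD difference and normal data, adjustment is not materially worse than either unadjusted reading at any correlation examined. It helps clearly from about r = 0.5: 72 to 76% power, against 61 to 62%. Below about 0.3 the gain over final values is slight, and at 0.7 or more rank ANCOVA adds little to change scores. With marked skew and an uninformative baseline, ANCOVA on the raw scale can lose about 4 points, which is one reason to keep a rank-based sensitivity analysis.

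The sizes rest on the assumed effect, distribution and correlations. That the quantity is undefined and the adjustment absent rests on the text alone. Nothing here shows the planned test to be invalid, or that the trial's overall conclusion would change.

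**What to change.** In section 8.3.1:

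1. For goblet cell density and the comfort index (primary), and also for IOP and tear break-up time (secondary), prespecify ANCOVA of the final value on treatment with the baseline value as covariate. Report the adjusted difference with its 95% CI.
2. Name one rank-based sensitivity analysis in advance, either Quade rank ANCOVA or Mann-Whitney. If Mann-Whitney, state whether it is run on final values or changes. Do not switch the primary method on residuals or on the planned Kolmogorov-Smirnov test: at 24 subjects that is a data-dependent choice, and Quade's method does not directly give the adjusted difference and interval.
3. Define baseline as the last value recorded before the first application of study product on day 1. A cut-off at opening of the allocation envelope should be avoided. Section 6.5.1.2 lists assignment ahead of the comfort index and cytology, so such a cut-off could discard their only scheduled baseline. The definition also settles which value counts where both screening and basal measurements exist.

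The cost is plan wording only: no added subjects, visits or measurements, and ANCOVA is available in SPSS.

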# 6.4 Outcome variables

# 6.4.1 Security variables

# 6.4.1.1 Primary outcome variables

- Globet cell density
- Epithelial defects in cornea and conjunctiva.
- Presence of adverse events.

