#### 6.4.1.2 Primary outcome variables of tolerability

- Burning
- Foreign body sensation
- Itching
- Eye comfort index

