6.4.3 Methods and scales to be used for the measurement of the variables

Variable	Unit	Symbolo	Type	Method of measurement	Normal value
Age	years		Continuous	Calculation from the day of birth	NA
Gender	Female/ Male	F/M	Nominal	Direct questioning	NA
Adverse events	Number of cases	n	Discreet	Conteo	NA
Intraocular presure	Milimeters of mercury	mmHg	Continuous	Goldman's applanation tonometry	11 - 21
Visual ability	Fraction	Snellen	Nominal	Chart	
Tear rupture time	Seconds	S	Continuous	Direct counting	> 10
Eye confort index	Points		Discreet	Questioning	
Adverse events	Present / Absent		Nominal	Comprehensive assessment	Absent
Goblet cell density	Cells per square milimeter	Cel/mm 	Continuous	Citology per impression	> 500 cell/mm
ital signs					
Heart rate	Beats per minute	lpm	Discreet	Auscultation	60 – 100
Breathing frequency	Breaths per minute	rpm	Discreet	Auscultation	12 – 24
Systemic blood pressure	Milimeters of mercury	mmHg	Continuous	Non-invasive auscultatory measurement	< 120 / 80
nterior segment					
Epithelial defects	Degrees		Discreet	Direct observation with green lysine and fluorescein stains	Oxford Scale
)phthalmologic signs an	d symptoms				
Conjunctival hiperemia	Normal / Very Light / Mild / Moderate / Severe		Ordinal	Direct observation.  Classification of Efron	Normal
Chemosis	Present / Away		Nominal	Direct observation	Absent
Burning	Severity: Absent, very mild, mild,		Nominal	Direct questioning	Absent

Version: 1.0

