# **CONFIDENTIAL**

Variable	Unit	Symbolo	Туре	Method of measurement	Normal value
	moderate and severe				
	Frequency: At all times, almost at all times, 50% of the time, almost in no time, at any time.				
	Severity: Absent, very mild, mild, moderate and severe				
Foreign body sensation	Frequency: At all times, almost at all times, 50% of the time, almost in no time, at any time		Nominal	Direct questioning	Absent
Pruritus	Severity: Absent, very mild, mild, moderate and severe Frequency: At all times, almost at all times, 50% of the time, almost in no time, at any time	-	Nominal	Direct questioning	Absent
Post-application sympto					
Burning	Present / Away		Nominal	Journal of the subject	Absent
Sensación de cuerpo extraño	Present / Away		Nominal	Journal of the subject	Absent
Prurito	Present / Away		Nominal	Journal of the subject	Absent
Ojo rojo (síntoma)	Present / Away		Nominal	Journal of the subject	Absent
posterior segment					
Macula	Normal / Abnormal		Nominal	Direct observation	Normal
Optical disk integrity	Normal / Abnormal		Nominal	Direct observation	Normal
Blood count					
Erythrocytes		M/uL	Continuous		

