#### 6.4.3.9 Ocular symptomatology

The subject will be questioned directly about the presence in general (since the last visit) of the following symptoms: burning, foreign body sensation and pruritus. Respond about the severity and frequency of symptoms such as:

Severity: Absent (0), very mild (1), mild (2), moderate (3) and severe (4)

Frequency: At all times (4), almost at all times (3), 50% of the time (2), almost at no time (1), at any time (0).

The number corresponding to each symptom will be registered in the CRF.

Post-application symptomology:

The subject will be requested, that in the subject's daily instrument, after registering the application of the product under investigation, mark YES or NO according to the presence of the following symptoms: burning, sensation of a foreign body, red eye and pruritus

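### Primary symptoms graded 0 to 4 are sent to 2x2 chi-square tables with no stated cut, scale or primary version; absent versus present, the likeliest reading, discards the grading

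*Combined protocol and SAP*

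**What the plan says.** - **Outcomes.** Section 6.4.1.2, "Primary outcome variables of tolerability", lists burning, foreign-body sensation, itching and the eye comfort index. Section 6.4.1.1 lists "Epithelial defects in cornea and conjunctiva" among the primary safety outcomes.
- **Visit scores.** Section 6.4.3.9 has each symptom graded at visits as "Severity: Absent (0), very mild (1), mild (2), moderate (3) and severe (4", and separately on a five-level frequency scale, also coded 0 to 4.
- **Diary.** The same section asks the subject, after each application, to "mark YES or NO according to the presence of the following symptoms: burning, sensation of a foreign body, red eye and pruritus".
- **Variable types.** Table 4 lists the levels ("Severity: Absent, very mild, mild, moderate and severe") but types the symptoms *Nominal*, with normal value Absent. Conjunctival hyperemia ("Normal / Very Light / Mild / Moderate / Severe") is typed *Ordinal*. Epithelial defects ("Direct observation with green lysine and fluorescein stains", graded on the Oxford scale) and the eye comfort index are typed *Discreet*.
- **Tests in section 8.3.1.** Continuous quantitative variables get Wilcoxon within arms and Mann-Whitney between arms. For nominal and ordinal qualitative variables the analysis "will be done creating 2x2 contingency tables and it will be carried out in the following way": McNemar or Pearson within arms, Pearson chi-square between arms.
- **Tests in the Summary (section 1).** Quantitative variables without restriction get Mann-Whitney, and qualitative variables get chi-square with no mention of a 2x2 layout.
- **Verdict.** Section 8.3.1 calls the product safe and tolerable when the primary outcomes show no clinical and statistical differences from the comparator.

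**The concern.** A five-level score fits a 2x2 table only after it has been split in two, and the plan gives no split. It also leaves open whether the visit score or the diary is the primary version and, for the visit score, whether severity or frequency is analysed. Because the verdict rewards finding no difference, a cut that is insensitive to the actual pattern favours the product. If the cut is chosen after the data are seen, including the data of the 8-subject partial analysis in section 8.3.2, the choice can produce the statistical half of a favourable result.

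A smaller gap sits beside this one. The Oxford grade and the eye comfort index are primary but *Discreet*, a type that section 8.3.1 does not name. Under the Summary they would go to Mann-Whitney. The Oxford grade could equally be read as ordinal, which would send it to the 2x2 tables.

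**Working it through.** The plan has no figure of its own to reproduce here. The inputs from the documents are 12 subjects per arm (section 6.6), alpha 0.05 and Pearson chi-square (section 8.3.1), and the 0 to 4 scale (section 6.4.3.9). The documents give no symptom distributions, so those below are assumptions.

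**1. Constructed example.** Comparator: 4 absent, 8 very mild. PRO-167: 4 absent, 4 moderate, 4 severe. For a 2x2 table with cells a, b, c, d, chi-square = N(ad − bc)² / (product of the four margins), uncorrected.

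- Any symptom, 8 v 8: chi-square 0, p = 1.00.
- Mild or worse, 0 v 8: 24 × (0×4 − 12×8)² / (12×12×8×16) = 221,184 / 18,432 = 12.0, p = 0.0005. Moderate or worse gives the same table.
- Severe, 0 v 4: 24 × (0×8 − 12×4)² / (12×12×4×20) = 55,296 / 11,520 = 4.8, p = 0.028. The smallest expected count is 4×12/24 = 2, and Fisher's exact test gives 0.093.
- Chi-square on all occupied grades, as the Summary would allow: expected counts are 4, 4, 2 and 2 in each arm, so the statistic is 0 + 2×(4²/4) + 2×(2²/2) + 2×(2²/2) = 16 on 3 df, p = 0.001.
- Mann-Whitney on the full score: PRO-167 is worse in 8×12 = 96 of 144 pairs and tied in 4×4 = 16, so P(worse) = (96 + 8)/144 = 0.72 (95% CI 0.49 to 0.96). Tie-corrected p = 0.054, exact p = 0.066.

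**2. How often the cut matters.** Simulation: 200,000 trials per scenario, 12 per arm, two-sided 0.05, uncorrected Pearson chi-square and tie-corrected Mann-Whitney. *Disagree* means that the cuts any, mild or worse, and moderate or worse do not all give the same answer on p ≤ 0.05.

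| Assumed % at grades 0-4, comparator v PRO-167 | Power: any / mild+ / moderate+ | Mann-Whitney | Disagree |
|---|---|---|---|
| A, large: 40/40/15/5/0 v 15/20/25/25/15 | 27 / 67 / 55% | 67% | 62% |
| B, large: 80/15/5/0/0 v 40/30/20/10/0 | 57 / 32 / 3% | 57% | 62% |
| C, large, high grades only: 30/50/15/5/0 v 30/10/20/20/20 | 5 / 57 / 55% | 32% | 70% |
| Mild: 80/15/5/0/0 v 65/25/8/2/0 | 12 / 2 / 0% | 12% | 13% |
| Mild: 90/10/0/0/0 v 75/20/5/0/0 | 12 / 0 / 0% | 12% | 12% |
| Mild: 70/20/10/0/0 v 50/30/15/5/0 | 19 / 7 / 0% | 17% | 22% |

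With identical arms (40/40/15/5/0, 80/10/5/3/2 and 15/20/25/25/15) the cuts disagree in 9%, 5% and 12% of trials, and Mann-Whitney rejects in 4 to 5%. With Fisher's test instead of Pearson, disagreement in A, B and C is 55%, 44% and 52%.

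**3. Baseline adjustment (secondary).** 40,000 bivariate-normal trials per assumed baseline-to-final correlation, true difference 1 SD, 12 per arm. Power at correlations 0.3 / 0.5 / 0.7:

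- ANCOVA: 67 / 75 / 89%
- rank ANCOVA: 65 / 72 / 85%
- Mann-Whitney on the final value: about 63% throughout
- Mann-Whitney on the change: 49 / 63 / 84%

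Type I error is 4.9 to 5.4% for all of these.

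**The case against.** **Absent versus present is the implied cut.** The *Nominal* type, the normal value Absent and the 2x2 layout together make this the likeliest reading. But a normal value is not an analysis rule, and this is the cut that returns p = 1.00 in the example and 5% power in scenario C.

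**The Summary allows an uncut table.** This is correct: the absence of a cut is a fault only under section 8.3.1. The two sections still prescribe different analyses, and an unordered chi-square ignores the order of the grades.

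**The analysts are blinded (sections 7.4 and 8.3.1).** This protects in part. The arms are still coded as separate groups, so the analyst can see whether a cut separates them.

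**The trial is exploratory, in healthy subjects.** Large contrasts may be unlikely. A reader might infer that the cut will often decide the result, but the 62 to 70% figures rest on large assumed effects and the documents do not support *often*. A reader might also count 2 scales × 4 cuts × 2 post-baseline visits = 16 open tables per symptom. Section 6.4.4 already has outcomes evaluated at each visit, so the visits are not a free choice. What is missing is which visit carries the verdict.

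**The verdict may not turn on a p-value.** The rule can be read as failing the product only when a difference is both clinical and statistical. On that reading a cut-driven p-value alone does not settle the verdict.

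**The rank test is not always better.** This stands. It narrowly misses 0.05 in the example and has 32% power in scenario C, against 57% for the cut at mild or worse.

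**Conclusion.** The gap is real and should be closed: the plan names no cut, scale or primary version for three primary outcomes, and the likeliest default throws away the grading. The cut can change the statistical result. Under the assumed distributions the three cuts disagree in about 5 to 12% of trials with identical arms, 12 to 22% with mild contrasts and 62 to 70% with large ones.

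The point about *Discreet* outcomes is minor. A reader might infer that the Oxford grade and eye comfort index have no planned test at all. The Summary gives Mann-Whitney to all quantitative variables, so the supported statement is only that section 8.3.1 does not clearly assign one.

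The baseline point concerns precision only. The planned Mann-Whitney test is valid, and at a correlation of about 0.3 the gain is small: 66.9% for ANCOVA against 65.1% for an unadjusted t-test.

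**What to change.** In section 8.3.1 and Table 4:

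1. Retype the graded symptoms and the Oxford grade as ordinal. Name the primary symptom version (visit score or diary), the scale, and the visit that carries the verdict.
2. Compare arms on the full score with a tie-corrected or exact Mann-Whitney test. Give an effect estimate, such as the probability that a PRO-167 subject scores worse, with a confidence interval. Show frequencies by full grade and arm. Treat hyperemia the same way.
3. If a supporting cut is wanted, name it before any data are seen, including the partial analysis, and state that it is descriptive and does not enter the verdict.
4. Keep 2x2 tables for truly binary items (diary answers, chemosis, adverse event present or absent), with Fisher's exact test where expected counts are small.
5. Make the Summary and section 8.3.1 agree by extending Mann-Whitney in 8.3.1 to discrete scores.
6. Secondary: for goblet-cell density, eye comfort index, intraocular pressure and tear break-up time, use the baseline already scheduled in section 6.5 as a covariate (ANCOVA or rank ANCOVA). Otherwise, state whether Mann-Whitney uses the final value or the change.

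The cost is wording and a little programming, with no new visits, subjects or data. The price of the rank test is lost power when a shift is confined to the higher grades (scenario C). The tables by full grade and any pre-named descriptive cut would keep such a pattern visible.
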